#### **9.4.7 Lack of Efficacy**

Not applicable.

### **9.5 Additional Reporting Requirements for Serious Adverse Events**

#### **9.5.1 Investigator Reporting Responsibilities**

Any Serious Adverse Event (SAE) must be reported to LEO on the (paper) Serious Adverse Event Form – Clinical Trials within 24 hours of first knowledge. This report should contain an assessment of available information on seriousness, severity, causal relationship to the investigational product, comparator or trial procedure, the action taken, the outcome to date, and a narrative description of the course of the event.

The completed SAE form must be faxed or scanned and e-mailed to Global Pharmacovigilance, LEO using the following fax number or e-mail address:

[contact] (for Global Pharmacovigilance)

E-mail address: [[contact]](mailto:[contact]) (for Global Pharmacovigilance).

It may be relevant for the (sub)investigator to enclose other information with the SAE form, such as reports of diagnostic procedures, hospital records, autopsy reports, etc.

Additionally, Global Pharmacovigilance, LEO may request further information in order to fully assess the SAE. The (sub)investigator must forward such information to Global Pharmacovigilance, LEO upon request by fax or e-mail (see contact details above).

The investigator must notify the local IRB(s)/IEC(s) of SAEs as required by current applicable legislation for the concerned country.

SAEs occurring after the completion of the clinical trial including any protocol required post-treatment follow-up period should not be routinely sought or collected. However, such events should be reported to Global Pharmacovigilance, LEO ([contact]) if the (sub)investigator becomes aware of them.

The criteria qualifying the AE to be an SAE should be recorded in the CRF (see section [26.2, Appendix 2](#)).

### **9.5.2 LEO Reporting Responsibilities**

Global Pharmacovigilance, LEO is responsible for assessing whether or not an SAE is expected. The relevant reference documents for this clinical trial are:

For the investigational product, the Investigator's Brochure, edition 5 and subsequent updates must be used ([14](#)).

For CORTROSYN® (used in the US), the latest version of the US Prescribing Information (USPI) must be used .

For Synacthen® (used in Europe) the subsequent updated SmPC for Synacthen® must be used.

Global Pharmacovigilance, LEO will notify the regulatory authorities and concerned investigators of SAEs according to the current applicable legislation for the concerned countries.

The IRB(s)/IEC(s) will be notified of SAEs according to the current applicable legislation for the concerned countries.

All SAEs that are assessed as causally related to the investigational product(s) by either the investigator or LEO, and which are not expected (Suspected, Unexpected Serious Adverse Reactions (SUSARs)) are subject to expedited reporting to regulatory authorities and IRB(s)/IEC(s) according to the current applicable legislation in the concerned countries. Investigators will be notified of these on an ongoing basis.

## 9.6 Follow-up for Final Outcome of Adverse Events

During the trial, the investigator should follow up for final outcome on all AEs (including SAEs). Once a subject leaves the clinical trial, the investigator should follow up on the outcome of all non-serious AEs classified as of possible/probable relationship to the investigational product for  $14 \pm 2$  days or until the final outcome is determined, whichever comes first. SAEs must be followed up until a final outcome has been established, i.e. the follow-up may continue beyond the end of the clinical trial.

## 10 Investigational Product(s)

### 10.1 Investigational Product Description

**Table 15: LEO 90100**

Finished product (brand) name (if available)/name Investigational Product	LEO 90100
Formulation	Aerosol, foam
Active ingredient name/concentration	Calcipotriol 50 mcg/g (as hydrate) and betamethasone 0.5 mg/g (as dipropionate)
Development Number	CCI [REDACTED]
Excipients [not quantitative]	White soft paraffin Liquid paraffin Polyoxypropylene-11 stearyl ether all-rac-alpha-tocopherol Dimethyl ether Butane Butylhydroxytoluene (E321) (CCI [REDACTED] [REDACTED])
Pack size(s)	60 g (net weight excluding propellants)
Manufacturer of bulk IP (ointment intermediate)	LEO Laboratories Ltd., [name]
Manufacturer of IP in primary packaging	Colep Laupheim GmbH & Co. KG [name]
Release testing of IP in primary packaging	LEO Pharma A/S, [name]
Manufacturer of secondary packaging and labelling	CCI [REDACTED]
Certifier of secondary packaging and labelling	CCI [REDACTED]

## 10.2 Administration of Investigational Products

**Table 16: Administration of IP**

Route of administration	Topical
Dosing frequency	Once daily
Time of day for dosing	No specific requirements
Relation of time of dosing to dietary intake	No specific requirements
Relation of time of dosing to clinical assessments	No dosing within 24 hours of Day 14 (Visit 2) and Day 28 (Visit 3) Investigational product will be applied at Visit 2 and Visit 3 under supervision of site staff after all clinical assessment have been conducted

The investigational product (IP) must be dispensed by the (sub)investigator/investigational staff at Visit(s) 1 and 2. The subject and/or parents/legal guardian should be instructed to return all dispensed investigational product (used and unused cans) at the following visit.

At Visit 1 the subject and/or parents/legal guardian will be carefully instructed (verbally and in writing by handing over a subject treatment instruction sheet) on how to apply the IP at home. The first application of the IP should be made by the subject and/or parents/legal guardian itself under supervision of the site staff. At the days of trial visits (Visit 2 and Visit 3) however, the application of IP will be done on site under supervision of site staff.

The medication should be sprayed directly on the skin at a distance of 3 to 10 cm. The foam should be gently spread with the fingertips until the medication is absorbed. The aerosol foam should be shaken before use and can be sprayed holding the can in any orientation except horizontally.

The (sub)investigator will have the discretion to determine the number of cans required to be dispensed at each dispensing visit (Visits 1 and 2).

As a guidance for the (sub)investigator the maximum weekly dose will be determined by the age and BSA at Visit 1:

- For subjects aged 12 to < 15 years with a BSA  $\leq 1.3 \text{ m}^2$ , 2 cans should be dispensed for the treatment period of 14 days.
- For subjects aged 12 to < 15 years with a BSA  $> 1.3 \text{ m}^2$  and subjects aged  $> 15$  years with a BSA  $\leq 1.7 \text{ m}^2$ , 3 cans should be dispensed for the treatment period of 14 days.
- For subjects aged  $> 15$  years with a BSA  $> 1.7 \text{ m}^2$ , 4 cans should be dispensed for the treatment period of 14 days.

The BSA will be calculated using the Mosteller formula ([Appendix 9](#)).

Subjects taking part in the HPA axis / Pk assessments:

For subjects performing HPA axis and PK assessments, being treated under maximal use conditions, a maximum weekly dose will not be established. The (sub)investigator is to ensure the subject has enough investigational product to apply to all affected areas of the body and scalp once daily.

### **10.3 Precautions/Overdosage**

Overdose with calcipotriol may be associated with hypercalcaemia. Clinically important hypercalcaemia will be managed at the investigator's discretion with rehydration, bisphosphonate administration or according to local standard of care. Hypercalcaemia should rapidly subside when treatment is discontinued.

Overdose with corticosteroid containing products may result in suppression of adrenal function which is usually reversible. In such cases, symptomatic treatment is indicated. In case of chronic toxicity, corticosteroid treatment must be discontinued gradually.

### **10.4 Packaging of Investigational Products**

#### **Individual Visit Kits**

Individual cans containing LEO 90100 will be dispensed at each visit by the site. The number of cans dispensed at each visit is dependent on the subject's age and BSA at Visit 1. Each single can will be labelled with a unique kit number and packed in a covering carton.

#### **Immediate Treatment Packaging - Individual Unit (Cans)**

The primary packaging for LEO 90100 aerosol foam consists of an aluminium can into which the formulation is pre-filled and subsequently administered through a continuous valve.

Each individual unit contains 60 g of Investigational Product.

The labelling of trial products must be in accordance with European Union (EU) Annex 13, local regulations and trial requirements.

## 10.5 Storage of Investigational Products

All LEO supplied drugs must be stored in a secure and restricted area under the conditions specified on the label and remain in the original container until dispensed.

Furthermore, the following storage conditions and handling precautions should be observed:

### LEO 90100 aerosol foam:

- Shake before use
- Wash hands before and after use
- Keep away from heats/sparks/open flames/hot surfaces/sunlight
- Keep out of the reach of children
- Do not inhale
- Do not smoke
- Do not exceed temperatures above 50°C (122°F)
- Do not pierce or burn, even after use
- EU storage conditions: Store at 2°C (35.6°F) to 25°C (77°F). Do not freeze
- US storage conditions: Store at 20°C (68°F) to 25°C (77°F). Excursions between 15°C to 30°C permitted. Do not freeze

## 10.6 Treatment Assignment

Subjects who have been found to comply with all the protocol's inclusion and exclusion criteria will start treatment and be dispensed with investigational product at Visit 1. Each can will have a unique kit number. When a can is dispensed to the subject, the unique kit number for that can will be recorded in the subject's medical record and the CRF.

### 10.6.1 Randomisation Code List

Not applicable.

## 10.7 Non-Investigational Medicinal Products

### 10.7.1 CORTROSYN® (cosyntropin)/Synacthen® for injection

CORTROSYN® (used in the US) is a commercial solution for injection containing cosyntropin that will be used for the ACTH-challenge test. One ampoule contains cosyntropin PhEur 250 micrograms (equivalent to 25 IU ACTH).

Synacthen® (used in Europe) is a commercial solution for injection containing tetracosactidhexaacetate that will be used for the ACTH challenge test. One ampoule contains 1 ml of 0.28 mg tetracosactid-hexaacetate (0.25 mg tetracosactid which equals 25 IU ACTH).

CORTROSYN®/Synacthen® will be sourced by the investigational sites.

CORTROSYN® will be used in accordance with the USPI for the marketed product . Synacthen® will be used in accordance with the subsequent updated SmPC.

**Table 17: CORTROSYN® (used in the US)**

Finished product (brand) name (if available)/name investigational product	CORTROSYN® (cosyntropin) for Injection
Formulation	Sterile lyophilized powder to be reconstituted with 0.9% Sodium Chloride Injection, USP
Active ingredient name/concentration	Cosyntropin ( $\alpha$ 1-24 corticotropin); 0.25mg per vial
Excipients	Mannitol, glacial acetic acid and sodium chloride. It contains no antimicrobial preservative.
Pack size(s)	Box of 10 vials of CORTROSYN® (cosyntropin) for Injection
Manufacturer's name	Amphastar Pharmaceuticals, Inc. Rancho Cucamonga, CA 91730 U.S.A.
Supplier's name	Not Applicable.
Certifier's name	Amphastar Pharmaceuticals, Inc. Rancho Cucamonga, CA 91730 U.S.A.

**Table 18: Synacthen® (used in Europe)**

Finished product (brand) name (if available)/name investigational product	Synacthen®
Formulation	Solution for injection
Active ingredient name/concentration	Tetracosactid 0.25 mg/mL (i.e., 25 IU ACTH)
Excipients	Acetic acid, sodium acetate, sodium chloride, aqua ad inject.
Pack size(s)	Ampoules: 10 times 1 ml
Manufacturer's name	Products available on the local market will be used (according to the local marketing authorisation) To be sourced individually by sites (excluding Poland and Romania)
Supplier's name	See above
Certifier's name	See above

### 10.7.1.1 Packaging and Labelling

The marketed product, as available in the US or in Europe will be used for this study without any re-labelling or re-packaging of the product. US and the Netherlands will be responsible for purchasing the CORTROSYN®/Synacthen®, they will be reimbursed for the non-investigational IP. Poland and Romania will be provided the Synacthen® through the depot Catalent in Bathgate, UK.

### 10.7.1.2 Storage of Non-Investigational Medicinal Products

CORTROSYN®/Synacthen® should be stored in a safe and secure place inaccessible for children. The temperature for storage should be 15 to 30°C for CORTROSYN®. Synacthen® should be protected from light and stored in a refrigerator (2 - 8°C). The Investigator is responsible for ensuring that the storage of CORTROSYN®/Synacthen® is in accordance with these conditions. Should there be any evidence that these conditions have not been maintained, the product should be destroyed and spoiled stock replaced.

### 10.7.1.3 Reconstitution and Administration

For CORTROSYN®/Synacthen® the contents of one vial (0.25mg of CORTROSYN®) should be reconstituted in 2 to 5ml of 0.9% Sodium Chloride Injection, USP, and injected intravenously over a 2-minute period. The reconstituted drug product should be inspected visually for particulate matter and discoloration prior to injection. Reconstituted CORTROSYN®/Synacthen® should be used promptly and should not be retained. Any unused portion should be discarded.

#### **10.7.1.4 Precautions**

Prior to injection of CORTROSYN®/Synacthen®, the investigator and staff must be prepared to treat any possible anaphylactic/allergic/hypersensitivity reaction. Severe anaphylactic reactions to CORTROSYN®/Synacthen® can be minimised by discontinuing the IV injection at the earliest sign of any local or general reaction such as redness, urticaria, pruritus, flushing of the face, malaise or dyspnoea. In the rare event of a serious allergic/anaphylactic reaction, local procedures should be followed and IM/IV epinephrine (adrenaline), IV high dose corticosteroids, IV antihistamines and intravenous fluids must be readily available and immediately used as appropriate. Protection of the airway must also be considered and managed appropriately.

Because of the risk of an allergic reaction, the injections should be given under medical supervision and the subject kept under observation for approximately one hour. If subjects experience an allergic reaction to CORTROSYN®/Synacthen® they should be withdrawn from the trial. Repeat administration may increase the risk of hypersensitivity. Subjects should be instructed to inform subsequent physicians of previous use of corticotropin hormones (see the USPI for CORTROSYN® and the SmPC for Synacthen® for further details).

#### **10.7.2 0.9% Sodium Chloride Injection, USP**

0.9% Sodium Chloride Injection, USP will be sourced by the investigational sites in the US and Europe and reimbursed by LEO Pharma A/S. There is no requirement for a specific brand or manufacturer to be used.

0.9% Sodium Chloride Injection, USP will be used in accordance with the product monograph specific to the chosen product.

##### **10.7.2.1 Packaging and Labelling**

The marketed product, as available in the US and Europe will be used for this study without any re-labelling or re-packaging of the product.

##### **10.7.2.2 Storage**

The product should be stored in a safe and secure place inaccessible for children and in accordance with the manufacturer's instructions (e.g. product monograph or labels) specific to the chosen product.

### **10.7.2.3 Precautions**

Product specific precautions and handling instructions will be provided in the product monograph specific to the chosen product.

General precautions for use with 0.9% Sodium Chloride Injection, USP include:

- Do not use unless the solution is clear and seal intact.
- Do not re-use containers.
- Discard unused portion.

## **10.8 Drug Accountability and Compliance Checks**

### **10.8.1 Drug Accountability**

#### **10.8.1.1 Drug Accountability Investigational Product**

The investigator is fully responsible for the investigational products at the trial site, for maintaining adequate control of the investigational products, and for documenting all transactions with them.

Dispensing of investigational products may be delegated, e.g. to a hospital pharmacy, as locally applicable.

At each visit, the investigational product, including (empty) cans dispensed at the previous visit, must be returned by the subject. An inventory (Individual Drug Accountability Form) must be kept, tracking the investigational product given to and returned by each subject enrolled in the trial. This inventory must be available for inspection during monitoring visits and will be checked by the monitor to ensure correct dispensing of the investigational product.

All investigational products supplied by the Contract Manufacturing Organisation (CMO) on behalf of LEO must be returned to the CMO. Prior to their return, they must be fully accounted for by the monitor with the help of the person responsible for dispensing the investigational products. Accountability must be documented by using drug accountability forms.

Investigational products may be returned from the trial site either to the CMO directly or via the LEO Pharma A/S affiliate/CRO responsible for running the clinical trial.

The investigational product returned to the CMO will be reconciled with the Individual Drug Accountability Forms. All returned cans will subsequently be weighed by the CMO to determine the amount of the investigational product used.

### **10.8.1.2 Drug Accountability Non-Investigational Medicinal Products**

The investigator is fully responsible for the non-investigational medicinal products (i.e. CORTROSYN®/Synacthen® and 0.9% Sodium Chloride Injection) at the trial site. Dispensing of non-investigational medicinal products may be delegated, e.g. to a hospital pharmacy, as locally applicable.

The person responsible for dispensing the non-investigational medicinal products will be responsible for maintaining adequate control and for documenting all transactions. All non-investigational medicinal products sourced locally by the investigator (or designee) will be fully documented by use of (internal) drug accountability forms. An inventory will be kept of all non-investigational medicinal products dispensed for each subject in the trial. The batch number/lot number and expiry date of the non-investigational medicinal products dispensed will be recorded. This inventory must be available for inspection at monitoring visits and will be checked to ensure correct dispensing of non-investigational medicinal products.

### **10.8.2 Trial Product Destruction**

Used and unused trial products will be destroyed by the CMO according to LEO procedures.

### **10.8.3 Treatment Compliance**

At all on-treatment visits, the subject should be asked if she/he has used the investigational product as prescribed. If a subject is found to be non-compliant, the (sub)investigator should remind the subject of the importance of following the instructions given including taking the trial products as prescribed. The degree of non-compliance and the reason for it must be recorded in the CRF.

## **10.9 Emergency Unblinding of Individual Subject Treatment**

Not applicable.

## **11 Statistical Methods**

### **11.1 Determination of Sample Size**

The primary objective of the trial is to evaluate the safety of LEO 90100. No formal sample size calculation evaluating the power of the trial has been performed. However, a consideration regarding the sample size was made as described below.

For adverse events with a true (theoretical) frequency of at least 2% the probability of observing at least one case among the 100 subjects will be at least 86.7%.

## 11.2 Definition of Trial Analysis Sets

All subjects enrolled in the trial (i.e. subjects for whom informed consent has been obtained and who have been registered in a clinical trial) will be accounted for in the clinical trial report.

All subjects assigned treatment are included in the full analysis set and will be analysed for efficacy. Exclusions from the full analysis set can be considered in special cases as described in ICH E9, section 5.2.1., Full Analysis Set. If it is decided to exclude a subject assigned treatment from the full analysis set, a justification addressing ICH E9 will be given.

For the analysis of the results from the ACTH-challenge test, a per protocol analysis set will be defined by including subjects undergoing HPA axis assessments from the full analysis set, however excluding the subjects who:

- receive no treatment with the investigational product
- provide no results for the ACTH-challenge test at Week 4
- and/or do not fulfil the inclusion criterion concerning evidence of adrenal function at baseline (i.e. inclusion criterion 17).

A safety analysis set will be defined by excluding subjects from the full analysis set who either received no treatment with investigational product and/or for whom no post-baseline safety evaluations are available.

For the analysis of PK data, a PK analysis set will be defined by including subjects undergoing PK assessments from the full analysis set, however excluding the subjects who:

- receive no treatment with the investigational product.
- provide no PK data at Week 4.

The decisions regarding inclusion/exclusion of subjects and/or subject data from the trial analysis sets will be documented in the clinical trial report.

## 11.3 Statistical Analysis

### 11.3.1 Disposition of Subjects

The reasons for leaving the trial will be presented for all subjects assigned treatment by last visit attended.

### 11.3.2 Demographics and other Baseline Characteristics

Descriptive statistics of demographics and other baseline characteristics will be presented for all subjects assigned treatment and separately for per protocol analysis set. Presentations of age, sex, ethnicity, race and baseline disease severity according to the PGA on the body and scalp will also be given by centre.

Demographics include age, sex, race, ethnicity and skin type. Other baseline characteristics include height, weight and BMI, duration of plaque psoriasis, concurrent diagnoses (from medical history and indications for concomitant medication), concomitant medication, PGA on the body and scalp, PASI (calculated from the physician's assessment of extent and severity of the clinical signs), physician's assessment of extent of psoriasis vulgaris (total involvement as % of BSA, on trunk and/or limbs as % of BSA and on scalp as % of scalp area) and subject's global assessment of disease severity on the body and scalp.

### 11.3.3 Exposure and Treatment Compliance

The duration of exposure (weeks) and extent of exposure (subject-treatment-weeks) to IP will be summarised for safety analysis set.

The amount of IP used (g) and the average weekly amount of IP used (g) will be summarised for safety analysis set and also for per protocol analysis set and separately for three different treatment periods (the first two weeks, the second two weeks and the total treatment period). Furthermore, a plot of the average weekly amount of IP use over the total treatment period against baseline extent of total BSA involvement will be presented for both analysis sets.

The number and percentage of subjects who do and do not comply with the trial treatment instructions will be summarised for all subjects assigned treatment. The extent of non-compliance as categories of the percentage of applications missed (e.g.  $\leq 10\%$ ,  $> 10$  to  $20\%$ , etc.) will also be presented.

### 11.3.4 Analysis of Primary Endpoints

#### Adverse events

The number and percentage of subjects experiencing each type of adverse event will be tabulated for the safety analysis set. Further details are included in section [11.3.8.1](#).

#### Subjects with serum cortisol concentration of $\leq 18$ mcg/dl at 30 minutes after ACTH-challenge at Week 4

The analysis of the results from the ACTH-challenge test will be based on the per protocol analysis set.

The number and percentage of subjects with a serum cortisol concentration  $\leq 18$  mcg/dl at 30 minutes after ACTH-challenge at Week 4 will be tabulated.

The serum cortisol concentration at time 0 (just before the ACTH challenge) and at 30 and 60 minutes after ACTH-challenge at baseline (SV2) and Week 4, respectively, will be summarised.

The serum cortisol concentration at time 0 (just before the ACTH challenge) and at 30 and 60 minutes after ACTH-challenge and also the change in serum cortisol from time 0 to 30 minutes and 60 minutes recorded at baseline (SV2), Week 4 and FU2, respectively, will be listed for each subject with a value  $\leq 18$  mcg/dl at either 30 or 60 minutes after ACTH-challenge. Values  $\leq 18$  mcg/dl at 30 or 60 minutes after ACTH-challenge will be flagged.

#### Change in albumin-corrected serum calcium from baseline (SV2) to Week 4

The analysis of the albumin-corrected serum calcium data will be based on the safety analysis set.

For the albumin-corrected serum calcium, the absolute value by visit and at end of treatment and the change from baseline (SV2) to Week 4 and to end of treatment will be summarised. Furthermore, the 95% confidence interval (CI) of mean change from baseline to Week 4 and to end of treatment will be presented. In addition, the albumin-corrected serum calcium will be classified as ‘low’, ‘normal’ or ‘high’, depending on whether the value is below, within or above the reference range, respectively. Shift table will be produced showing the categories at baseline (SV2) against those at Week 4 and at end of treatment.

Summary tables and shift table will be repeated subgrouped by baseline 25-hydroxy vitamin D classifications (‘low’, ‘normal’ or ‘high’ with respect to its reference range).

Plots of the average weekly amount of IP use over the total treatment period against change from baseline to Week 4 and against change from baseline to end of treatment in albumin-corrected serum calcium will be presented.

The albumin-corrected serum calcium will be listed by visit for all subjects with the values out of reference range at any visit. Values outside the reference range will be flagged.

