## 6.2 Sample Size

The sample size was outlined in the Pediatric Study Plan for LEO 90100 and accepted by the FDA as an adequate sample size.

Enrolment of subjects will continue until data from 100 subjects are available for evaluation of the effect of LEO 90100 on calcium metabolism (i.e. the measurement of the serum calcium concentration is available before and at Visit 3). Therefore, the number of enrolled subjects can exceed 100 subjects.

The 100 subjects include the enrolment of 30 evaluable subjects in the assigned sites without adrenal suppression at baseline who undergo an ACTH-challenge test and PK assessments at end of treatment (Visit 3). At the time the sponsor confirms 30 evaluable subjects has been obtained, there may be other subjects ongoing in the trial that have not yet had an ACTH-challenge test and PK assessments. Such subjects will be allowed to complete the trial without an ACTH-challenge test and PK assessments.

Each centre should aim to enroll a minimum of three subjects. As the subjects are anticipated to be difficult to recruit, the suggested minimum number of subjects per centre is based on practical considerations rather than statistical robustness of estimates given per centre.

The statistical power considerations for this sample size are described in section [11.1](#).

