### Change in calcium:creatinine ratio from baseline (SV2) to Week 4 in spot urine

The analysis of the calcium:creatinine ratio in spot urine will be based on a subset of the safety analysis set including the subjects not undergoing HPA axis testing. The analysis will be performed as described for the analysis of the albumin-corrected serum calcium data in section [11.3.4](#).

### Subjects with ‘treatment success’ (i.e., ‘clear’ or ‘almost clear’ for subjects with at least ‘moderate’ disease at baseline, ‘clear’ for subjects with ‘mild’ disease at baseline) according to the physician’s global assessment of disease severity on the body at Week 4

The statistical analysis of efficacy will be based on the full analysis set. The percentage of subjects who achieve ‘treatment success’ according to the PGA on the body will be presented by visit and at end of treatment. The 95% CI, which is based on a binomial distribution, will be presented for the proportion of subjects with ‘treatment success’ at Week 4 and at end of treatment.

The percentage of subjects who achieve ‘treatment success’ according to the PGA on the body at Week 4 and at end of treatment will also be tabulated by age-group, sex, ethnicity, race, centre and baseline PGA on the body.

### Subjects with ‘treatment success’ (i.e., ‘clear’ or ‘almost clear’ for subjects with at least ‘moderate’ disease at baseline, ‘clear’ for subjects with ‘mild’ disease at baseline) according to the physician’s global assessment of disease severity on the scalp at Week 4

Subjects with ‘treatment success’ according to the PGA on the scalp will be analysed as outlined above for the body.

### Percentage change in PASI from baseline (V1) to Week 4

PASI is calculated using the formula given below based on the physician’s assessment of the extent and severity of the disease locally (head, trunk, arms, legs) [\(8.14\)](#).

The following formula will be used to calculate the PASI:

$$\text{Head } 0.1 (R + T + S)E = W$$

$$\text{Arms } 0.2 (R + T + S)E = X$$

$$\text{Trunk } 0.3 (R + T + S)E = Y$$

$$\text{Legs } 0.4 (R + T + S)E = Z$$

Where: R = score for redness; T = score for thickness; S = score for scaliness; E = score for extent

The sum of W + X + Y + Z gives the total PASI, which can range from 0 to 72.

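### The primary ACTH proportion, from 30 to 33 subjects, is planned without a confidence interval, although the secondary efficacy proportions and the calcium endpoints have one

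*Protocol*

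**What the plan says.** **ACTH endpoints.** Protocol 11.3.4 states: "The analysis of the results from the ACTH-challenge test will be based on the per protocol analysis set". For the primary endpoint, the number and percentage of subjects at or below 18 "mcg/dl at 30 minutes after ACTH-challenge at Week 4 will be tabulated". Cortisol concentrations at 0, 30 and 60 minutes are also summarised, and subjects with a low value at either time are listed with flags. Protocol 11.3.5 treats the secondary endpoint (low at both 30 and 60 minutes) in the same way. The Protocol Summary (Appendix 1) repeats the tabulation and leaves both proportions out of its list of results with a 95% interval.

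**SAP.** Section 6.3 adds no interval. In Appendix I, Tables 3-1 to 3-3 carry no interval note, whereas Tables 2-2, 2-13 and 3-5 do. Table 3-2 is titled for the both-times count. No table title names the 30-minute count.

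**Other endpoints.** For PGA success, Protocol 11.3.5 says: "The 95% CI, which is based on a binomial distribution, will be presented for the proportion of subjects", and success on the subject's global assessment is handled likewise. Serum calcium change and both 24-hour urine endpoints get a 95% interval for the mean change (11.3.4), as does the spot-urine ratio (11.3.5).

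**Sample size.** Protocol 6.2: "The 100 subjects include the enrolment of 30 evaluable subjects in the assigned sites without adrenal suppression at baseline". Protocol 11.1: "No formal sample size calculation evaluating the power of the trial has been performed". The one consideration offered there is about adverse events in the full cohort: "the probability of observing at least one case among the 100 subjects will be at least 86.7"% at a true frequency of 2%.

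**The concern.** HPA axis suppression is in the trial's title, and Protocol 3.4 counts it among the more serious potential effects of the steroid component. The endpoint that measures it is a single prespecified proportion from a cohort of about 30. Of the primary endpoints confined to that cohort, it is the only one without an interval.

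With so few subjects, the percentage alone says little about the rates that remain plausible. A result of none or one in 33 looks close to zero, and the reader is not shown the upper limit. The SAP suggests that the count is small: section 6.3 drops two planned tabulations for subjects with low cortisol because there were too few of them.

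There is a precedent for reading a zero count without a bound. Protocol 3.2.1 describes 0 of 35 adults with a low 30-minute cortisol in the earlier maximal-use trial as showing no indication of an HPA effect, and gives no interval. The exact upper limit for 0/35 is 10.0%.

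**Working it through.** **Inputs**

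- Planned ACTH cohort: n = 30 (Protocol 6.2).
- Achieved per protocol set: n = 33 (SAP 6.4.2, Table 2, 30-minute cortisol row).
- Confidence level: 95% (Protocol 11.3.10). Sidedness is not stated; two-sided is assumed.
- Number of subjects with low cortisol: not given in either document, so counts of 0 to 3 are shown.

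**Step 1. Reproduce the plan's own figure.** P(at least one case) = 1 − (1 − p)^n. With p = 0.02 and n = 100, this is 1 − 0.98^100 = 0.8674. The stated 86.7% is correct for what it describes.

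**Step 2. Exact (Clopper-Pearson) two-sided 95% limits for x of n.** Lower limit = the 0.025 quantile of Beta(x, n − x + 1), or 0 when x = 0. Upper limit = the 0.975 quantile of Beta(x + 1, n − x). For x = 0 the upper limit reduces to 1 − 0.025^(1/n): for n = 30 it is 0.1157, and for n = 33 it is 0.1058.

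| x | n = 30: % (95% CI) | n = 33: % (95% CI) |
|---|---|---|
| 0 | 0 (0 to 11.6) | 0 (0 to 10.6) |
| 1 | 3.3 (0.1 to 17.2) | 3.0 (0.1 to 15.8) |
| 2 | 6.7 (0.8 to 22.1) | 6.1 (0.7 to 20.2) |
| 3 | 10.0 (2.1 to 26.5) | 9.1 (1.9 to 24.3) |

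**Step 3. Sensitivity to the method.** For a zero count, Wilson two-sided upper limits are 11.4% (n = 30) and 10.4% (n = 33). One-sided exact 95% upper limits are 9.5% and 8.7%. The method hardly matters; sidedness moves the limit by about two percentage points.

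**Step 4. Same detection formula in the smaller cohort, as illustration only.** 1 − 0.98^30 = 0.455 and 1 − 0.98^33 = 0.487. The 2% benchmark belongs to adverse events; neither document names it as a suppression rate of interest.

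**Step 5. Intervals planned, side by side**

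| Endpoint | Role | 95% CI planned |
|---|---|---|
| Adverse events | Primary | No |
| Low cortisol at 30 minutes | Primary | No |
| Serum calcium change | Primary | Yes |
| 24-hour calcium excretion change | Primary, HPA cohort | Yes |
| 24-hour calcium:creatinine change | Primary, HPA cohort | Yes |
| Low cortisol at 30 and 60 minutes | Secondary | No |
| Spot-urine ratio change | Secondary | Yes |
| PGA and subject-assessed success (four proportions) | Secondary | Yes, binomial |

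**The case against.** The strongest reply is that the plan follows a convention: safety counts are tabulated, and efficacy proportions and mean changes get intervals. Adverse events are also a primary endpoint reported as percentages without an interval, so the ACTH endpoint was not singled out. That is correct. A reader who infers that ACTH is the only primary proportion without an interval would be wrong. What stands is that it is a single named binary endpoint in a small cohort, which is where an interval is most informative.

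A reader might also infer that the 86.7% is wrong or is being applied to the ACTH cohort. The documents do not support this. Section 11.1 limits the figure to adverse events among 100 subjects, says that no formal calculation was done, and makes no claim about the smaller cohort.

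A further tempting reading is that the design cannot exclude suppression rates of 10% or more. This is too loose: 0/33 excludes every rate above 10.6%, and on a one-sided 95% basis the limits for a zero count (9.5% and 8.7%) fall below 10%.

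The proportion is not reported in isolation. Cortisol summaries, individual data and retesting of subjects with low values are planned, and anyone given x and n can compute the interval. But summaries and listings do not bound the suppression rate, and leaving that to the reader is a weak substitute for reporting it. Finally, no decision rule or planned conclusion of no suppression appears in either document, and the adult wording in Protocol 3.2.1 concerns another trial and gives its denominator. The risk of over-reading is therefore an inference.

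**Conclusion.** The point holds as a reporting gap in a primary safety endpoint. It is not an error of calculation or design. Neither document plans an interval for the two ACTH proportions, while the rest of the plan does so for the efficacy proportions and the calcium changes. If the count is zero, suppression rates up to 11.6% (n = 30) or 10.6% (n = 33) remain compatible with the data; one case in 33 raises the limit to 15.8%, and two raise it to 20.2%. These limits assume an exact two-sided 95% interval and a denominator equal to the per protocol set. The observed count is not given, so the limit that will apply is not known from the documents. The missing SAP table for the 30-minute count is part of the same gap: an interval added only to the existing titled tables would miss the primary endpoint.

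**What to change.** 1. In the SAP, or in the trial report, present the two-sided exact (Clopper-Pearson) 95% interval with the proportion at or below 18 mcg/dl at 30 minutes, and with the proportion low at both 30 and 60 minutes.
2. Add a table to SAP Appendix I for the 30-minute count at Week 4 in the per protocol set, beside Table 3-2, each with an interval note like that under Table 2-2.
3. Label the interval as an addition. SAP section 5 says that the SAP was prepared after review of the data, and Protocol 11.3.10 provides for changes to be described in an amendment or the trial report.
4. Optionally, state the cohort's precision beside the result, for example that 0/30 is compatible with rates up to 11.6%. Protocol 11.1 can stay as it is.

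The cost is one table, a few words and a line of code. The endpoint and the data are unchanged. The reported precision will look less favourable.
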